The largest fibroid is defined as the fibroid which is the largest at baseline (measured by ultrasound). The fibroid identified at baseline as the largest will be followed up at each scheduled visit.

Fibroids volume measured by ultrasound (mL) $(2) \frac{\pi \times a \times b \times c}{6}$;

a = Largest diameter of the fibroid (cm), b = First diameter perpendicular to largest diameter (cm), c = Second diameter perpendicular to largest diameter (cm)

If only 2 diameters are available, the formula will be the same but the third diameter will be replaced by the mean of the available two diameters.

If only 1 diameter is available, the formula will be: $= \frac{4 \times \pi \times r^3}{3}$; $r = \frac{\text{available diameter of the fibroid (cm)}}{2}$

If one or two diameters are recorded as 0 cm, then those diameters will be considered missing and the rules above will apply.

Volume of 3 largest fibroids measured by ultrasound (mL)

Defined by the sum of the 3 largest fibroid volumes. If less than 3 fibroids are present, the volume of the actual number of fibroids will be summed. The 3 fibroids identified at baseline as the largest will be followed up at each scheduled visit.

Uterine volume measured by ultrasound (mL) $= \frac{\pi \times a \times b \times c}{6}$;

a = Maximum width anteroposterior of uterus (cm), b = Maximum width transverse (cm) of uterus, c = Corpus + cervix length (cm).

If only 1 or 2 diameters are available, the calculation will follow the same rules defined for fibroids volume measured by ultrasound.

Volume of the largest cyst (mL) $= \frac{\pi \times a \times b \times c}{6}$;

a = largest diameter of largest cyst (cm), b = diameter perpendicular to the largest cyst (cm), $c = \frac{a+b}{2}$ (cm)

If only 1 diameter is available, the calculation will follow the same rules defined for fibroids volume measured by ultrasound. If one diameter is recorded as 0 cm, then the value of the diameter will be considered missing and the rule above will apply.

BMD measurements

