6.2.3.3 Ultrasound examination related variables

- Percent change in volume of largest fibroid compared to baseline (baseline = last value obtained before randomization; measured by ultrasound examination)
- Percent change in volume of 3 largest fibroids compared to baseline (measured by ultrasound)
- Percent change in volume of uterus compared to baseline (measured by ultrasound)
- Percentage of subjects with a volume reduction of $\geq 25\%$ of the 3 largest fibroids (measured by ultrasound)
- Percentage of subjects with a volume reduction of $\geq 25\%$ of the largest fibroids (measured by ultrasound)
- Percentage of subjects with a reduction of $\geq 25\%$ of uterine volume (measured by ultrasound)

Analysis will be done by treatment group and visit/time interval B (according to [Figure 4-1](#)).

If multiple volume assessments by ultrasound are available for a time period, the smallest volume will be used for the baseline time period, and the largest volume will be used for any other time periods of Intervals B.

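### Volumes derived from one or two diameters may be compared with three-diameter volumes; depending on shape and on which axis is missing, that mismatch alone can exceed the 25% responder threshold

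*SAP*

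**What the plan says.** All the volume rules are in SAP section 4.5.

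- **Fibroid axes.** The diameters are defined relative to the longest one: "a = Largest diameter of the fibroid (cm), b = First diameter perpendicular to largest diameter (cm"), with c the second perpendicular. Volume is π·a·b·c/6.
- **Two diameters.** "the formula will be the same but the third diameter will be replaced by the mean of the available two diameters".
- **One diameter.** "If only 1 diameter is available, the formula will be" that of a sphere with the recorded diameter.
- **Zeros.** "If one or two diameters are recorded as 0 cm, then those diameters will be considered missing and the rules above will apply".
- **Uterus.** The ellipsoid formula is the same, but the axes are fixed anatomical dimensions: "a = Maximum width anteroposterior of uterus (cm), b = Maximum width transverse (cm) of uterus, c = Corpus + cervix length (cm"). For incomplete scans, "If only 1 or 2 diameters are available, the calculation will follow the same rules defined for fibroids volume measured by ultrasound".

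Section 6.2.3.3 uses these volumes for the uterus ("Percent change in volume of uterus compared to baseline (measured by ultrasound")), the largest fibroid and the three largest fibroids. Each is analysed as percent change and as the percentage of subjects with a reduction of at least 25%. If a period has several assessments, the smallest volume is taken at baseline and the largest in any later period.

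The SAP does not require the same diameters, or the same formula, at baseline and follow-up. It plans no analysis restricted to complete measurements and no count of volumes derived from incomplete ones.

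**The concern.** A percent change is meaningful only if numerator and denominator measure the same thing. Here one visit may use three measured axes and the other a sphere or a two-axis approximation. The difference between formulas then enters the percent change as if the organ had grown or shrunk.

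The uterus is the more exposed organ. Anteroposterior width, transverse width and length differ systematically, so the substitute depends on which axis happens to be available. For a fibroid, a is the largest diameter by definition, so a sphere built on it alone cannot be smaller than the three-diameter volume. An unchanged organ may be counted as a responder, a real reduction may be hidden, and a few extreme values may distort a group mean.

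**Working it through.** **Inputs.** The formulas and the 25% threshold come from SAP sections 4.5 and 6.2.3.3. The SAP gives no organ sizes and no frequency of missing diameters, so the dimensions below are assumptions. It states no figure of its own to reproduce.

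**Formulas.** The factor π/6 cancels in every ratio.
- Three diameters: V = (π/6)·a·b·c
- Two diameters: V = (π/6)·a·b·(a+b)/2
- One diameter: V = (4π/3)·(d/2)³ = (π/6)·d³

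**Unchanged uterus, 6 (anteroposterior) x 8 (transverse) x 10 (length) cm.** Full product 480, volume 251.3 mL.

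| Recorded at the incomplete visit | Product | Volume (mL) | Apparent change, follow-up incomplete | Apparent change, baseline incomplete |
|---|---|---|---|---|
| Anteroposterior + transverse | 6·8·7 = 336 | 175.9 | -30.0% | +42.9% |
| Anteroposterior + length | 6·10·8 = 480 | 251.3 | 0% | 0% |
| Transverse + length | 8·10·9 = 720 | 377.0 | +50.0% | -33.3% |
| Anteroposterior only | 6³ = 216 | 113.1 | -55.0% | +122.2% |
| Transverse only | 8³ = 512 | 268.1 | +6.7% | -6.3% |
| Length only | 10³ = 1000 | 523.6 | +108.3% | -52.0% |

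A true proportional reduction of 30% with the anteroposterior width missing at follow-up reads 0.70 x 720/480 - 1 = +5%, so a real responder is hidden.

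**Unchanged fibroid, 5 x 4 x 4 cm.** Full product 80, volume 41.9 mL.

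| Recorded at the incomplete visit | Product | Apparent change, follow-up incomplete | Apparent change, baseline incomplete |
|---|---|---|---|
| Largest + one perpendicular | 5·4·4.5 = 90 | +12.5% | -11.1% |
| Two perpendiculars | 4·4·4 = 64 | -20.0% | +25.0% |
| Largest only | 5³ = 125 (65.4 mL) | +56.3% | -36.0% |
| One perpendicular only | 4³ = 64 | -20.0% | +25.0% |

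With follow-up incomplete, this fibroid never becomes a false responder. It does when only its largest diameter was recorded at baseline (-36%). A true 30% shrinkage with only the largest diameter at follow-up reads 0.70 x 125/80 - 1 = +9.4%.

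**Dependence on shape.**
- Uterus, length missing at follow-up: -15.9% for 9 x 9.5 x 11 cm, -27.8% for 6 x 7 x 9, -40.9% for 6 x 7 x 11, -42.9% for 7 x 9 x 14.
- Near-round fibroid, 5 x 4.6 x 4.3 cm: -19.6% to +26.4% with follow-up incomplete and -20.9% to +24.4% with baseline incomplete, so no false responder either way.
- Elongated fibroid, 6 x 4 x 3 cm, largest diameter missing at follow-up: -41.7%.
- Sphere: 0% throughout.

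**General condition.** With two diameters at follow-up, the ratio to the full volume is the mean of the two recorded axes divided by the missing axis. An unchanged organ is therefore a false responder when the missing axis is at least 1/0.75 = 1.33 times that mean. With one diameter at follow-up, it is a false responder when that diameter is at most 0.75^(1/3) = 0.909 times the geometric mean of the three axes.

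**Same axes at both visits.** If every axis shrinks by a factor s, all three formulas scale by s³. An unchanged organ then gives exactly 0%, and a true proportional 30% reduction gives exactly -30%.

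**The case against.** The SAP's fallback is complete and reproducible, and section 4.3 gives the purpose of such rules as avoiding the exclusion of subjects. How the diameters are to be recorded at each scan may be settled in the protocol, which is not at hand. The rule for zeros is sensible: without it, one zero would make the volume zero and produce a spurious 100% reduction. Section 6.2.3.3 also has a conservative element in its smallest-at-baseline, largest-afterwards selection. The endpoints are other efficacy variables summarised descriptively, so neither BMD, the primary safety variable, nor the number of bleeding days, the secondary efficacy variable, is touched.

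Most of this stands, and it limits the point without removing it. The selection rule acts only when a period has more than one scan. It then makes false responders less likely but favours inflated follow-up volumes, which hides real reductions. A reproducible rule can still compare unlike quantities.

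A reader might infer that any missing diameter pushes the change past 25%. The tables show otherwise: 0% and +6.7% for two uterine gaps, and 12.5% or 20% in size for most fibroid gaps at follow-up. A reader might also infer that the responder rates are materially wrong or that the comparison between groups is biased. The SAP gives neither a frequency of missing diameters nor any reason for gaps to differ between groups, so neither can be concluded.

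**Conclusion.** The point holds in conditional form. The SAP allows volumes from different sets of diameters to be compared. For plausible but assumed shapes, this alone can cross the 25% threshold in either direction: -55% to +108% for the uterus and -20% to +56% for the fibroid used here, with follow-up incomplete and no true change. The uterus is the most exposed, elongated fibroids come next, and near-round fibroids are little affected. For the three-fibroid sum, a mismatch in one fibroid is diluted by the others.

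The number of misclassified subjects cannot be derived from the document. Because only descriptive other efficacy variables are involved, this is a minor, worthwhile correction and no threat to the trial's main conclusions.

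**What to change.** - **Uterus.** Compute percent change and 25% responder status from the same recorded axes at baseline and follow-up. Do not compare a one-axis sphere volume with a multi-axis volume; set that change to missing. Treat two-axis volumes that share only one axis in the same way.
- **Fibroids.** Base percent change and responder status on visits with three diameters at both time points. Matching axes is not a safe remedy here, because a, b and c are defined relative to the largest diameter at each scan and need not be the same physical axes. Keep the section 4.5 fallback volumes as a sensitivity analysis.
- **Selection within a period.** State the order of operations: restrict to eligible volumes first, then apply the smallest/largest rule of section 6.2.3.3.
- **Reporting.** Keep the single baseline volume for the baseline table in section 6.1.2. Report the number of volumes derived from fewer than three diameters by group and interval.

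**Cost.** A short change to the SAP text, some extra programming and one sensitivity table. A few subject-visits are lost from the main summary, more readily for the three-fibroid sum because each followed fibroid needs three diameters. For the uterus, the common-axis change is exact only if shrinkage is proportional across axes, and approximate otherwise.

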4.6 Blind Review

The results of the final data assessment will be documented in the final list of important deviations, validity findings and assignment to analysis set(s). Any changes to the statistical analysis prompted by the results of the review of study data will be documented in a SAP amendment and, if applicable, in a supplement to this SAP.

5. Analysis Sets

5.1 Assignment of analysis sets

Final decisions regarding the assignment of subjects to analysis sets will be made during the review of study data and documented in the final list of important deviations, validity findings and assignment to analysis set(s) (see Section 4.6).

Full analysis set (FAS): All subjects randomized to vilaprisan treatment groups, excluding randomized subjects who did not start TP 1 due to the study being temporarily paused and all subjects randomized to treatment group B will be included in the FAS. Subjects will be analyzed as randomized.

Safety analysis set (SAF): All subjects randomized to vilaprisan treatment groups who took at least 1 dose of study drug. will be included in the SAF. Subjects will be analyzed as treated.

All subjects randomized to treatment group B will be included in the SAF. Subjects will be analyzed as treated, regardless whether they actually took any medication (i.e., symptomatic, nonhormonal medical treatment).

Modified SAF: will include all subjects in the SAF without any validity findings which are those that may potentially affect the primary safety endpoint. Validity findings leading to exclusion from the modified SAF will be specified in the 'Specification of assessment criteria and identification requirements', which will be finalized before database lock. Subjects will be analyzed as treated.

All safety analyses will be performed on the SAF population. The FAS will be used for the display of all other variables. The analysis for the primary safety endpoint and all BMD related endpoints will be performed on the Modified SAF as well.

Screened subjects who are not included in the FAS will be used solely in disposition tables and will be listed only in Section 16 of the clinical study report, as described elsewhere.

6. Statistical Methodology

6.1 Population characteristics

In general, descriptive statistics will be presented for variables defined in this section. For continuous variables, number of observations, mean, standard deviation, minimum, median, and maximum will be presented. For categorical variables, number and percentage of subjects will be presented. Listings will be provided accordingly.

6.1.1 Subject validity, disposition

Study sample size (all enrolled), subject validity and reasons for excluding subjects from the analyses (all randomized), subject disposition (all enrolled) will be summarized by frequency tables. Enrolled means the subject signed the informed consent. The total number and percentage of subjects who prematurely discontinued each epoch with the reasons for discontinuation (all randomized), the number and percentage of subjects who performed adrenal monitoring, skin monitoring, endometrial monitoring and BMD within the safety closeout visit will be provided.

For the overall assessment of disposition, study completion means all phases of the study are completed up to and including the follow-up (FUP) visit.

6.1.2 Demographic, Baseline Characteristics

Demographics and baseline characteristics will be recorded during screening period. As specified in Section 4.5, the measurement closest to the administration of study drug will be used as baseline. All demographic and baseline characteristics will be listed and summarized by treatment and in total according to current existing BHC Global Standard Tables. The descriptive statistics will be presented for the SAF, modified SAF, and FAS.

Demographic and baseline assessments to be summarized will include:

- Age, region/ country and race, ethnicity
- Weight, height, body mass index (BMI)
- Categorized BMI group (<18.5, 18.5-<25, 25-<30, ≥30 kg/m²)
- Smoking and alcohol consumption
- Baseline BMD of lumbar spine, hip and femoral neck
- Baseline BMD of lumbar spine, hip and femoral neck by scan type (Lunar, Holgic and other)
- Baseline endometrial thickness
- Uterine fibroids visualized at baseline (Yes/No)
- The largest diameter of the largest fibroid, volume of largest fibroid, volume of 3 largest fibroids, location of largest fibroid (measured by ultrasound) at baseline. Baseline uterine volume, endometrial thickness (measured by ultrasound)
- Baseline MBL (by MP) and categorized MBL group (≤80 mL, 80< -150 mL, 150 <- 300 mL, 300 < - 500mL and >500 mL)
- Baseline hemoglobin
- Education (years of education, university/colleague degree)

6.1.3 Medical History

Medical history findings (ie, previous diagnoses, diseases or surgeries) will be coded by Medical Dictionary for Regulatory Activities (MedDRA) terms. Number and percentage of subjects with any medical history findings reported will be presented by primary system organ class (SOC) and preferred term (PT) based on the SAF.

All new or worsened findings after signing the informed consent should be documented on the AE eCRF page.

6.1.4 Reproductive and menstrual history

The reproductive history will include information on age at menarche, number of pregnancies, number of births, years since last birth or abortion (at any time and during the last 1 year) and duration of unsuccessful attempts (in months).

For number of pregnancies and number of births, not only the statistics based on continuous variables but also a frequency table based on each specific number recorded in CRF will be presented.

Reproductive history will be summarized for the SAF.

6.1.5 Uterine Fibroids relevant history

The uterine fibroids history includes information on family history, onset of symptoms, diagnosis, and previous medical treatments and procedures, if applicable. Reason for the initial diagnosis, symptoms/finding ever had/currently are collected as well.

Medical treatments relevant for uterine fibroids received ever/ during the last 6 months prior to the study and procedures for uterine fibroids (history, concurrent and planned) will be recorded and presented in this section. Procedures for uterine fibroids (concurrent) will be presented in section of other efficacy variables.

Uterine Fibroids relevant history will be summarized for the SAF.

6.1.6 Heavy menstrual bleeding questions

[figure not shown]
This set of questions has been developed as a tool to identify women with HMB. It could have been used at Visit 1 only and the responses could have been entered directly into the electronic data capturing system (RAVE), which is considered as primary source data. The questionnaire could also have been used as a pre-screening tool. The questions from this questionnaire will be summarized by a frequency table for the SAF.

6.1.7 Prior/Concomitant Medication

For prior/concomitant/post-treatment medications, the following definitions in accordance with the Global Standards Catalogue V4.0 will be used in the analysis (see [Figure 6-1](#)):

- Prior medication: Medication taken before start of the study drug intake (regardless of when it ended).
- Concomitant medication: Medication taken during Treatment phase, i.e. between first and last study drug intake (regardless of when it ended). In case it's not clear if a medication is prior, concomitant or post-treatment (for example, due to partially missing dates), medication will be classified as "concomitant".- Post-treatment medication: Medication taken after the Treatment phase, i.e. after last study drug intake.

Figure 6-1: Categories of medication (example)

Categories are prior medication (A, B, C), concomitant medication (B, C, D, E) and post-treatment medication (F). Source: Global Standards Catalogue V4.0

Medication, recorded as prior, concomitant or post-treatment medication in the eCRF, will be coded according to the World Health Organization Drug Dictionary WHODRUG GLOBAL B3 (initially September 1, 2017, within Bayer referred to as ‘2017SEP’), to the respective Drug Codes with their corresponding Anatomical Therapeutic Chemical (ATC) classification.

The number of subjects taking prior or concomitant medication will be analyzed using frequency tables based on classified data. Analysis of prior and concomitant medication will be done on the SAF.

Nonhormonal medical treatment for symptomatic uterine fibroids at/after the date of randomization for treatment group B will be recorded and coded to ATC codes according to the WHO Drug Dictionary. Subjects in treatment group B who took at least one nonhormonal symptomatic medical treatment will be summarized for prior/concomitant/post-treatment medications separately.

Nonhormonal symptomatic medical treatment:

- Analgesia producing opioids
- Benzodiazepines
- Nonsteroidal anti-inflammatory drugs (NSAIDs)
- Barbiturates and derivatives
- Benzodiazepine derivatives
- Adjunct antidepressant therapy
- Herbal antidepressants
- Monoamine oxidase A inhibitors
- Monoamine oxidase inhibitors, non-selective
- Non-selective monoamine reuptake inhibitors
- Other antidepressants
- Selective serotonin reuptake inhibitors
- Antifibrinolytics
- Blood coagulation factors

- Other haemostatics
- GnRH agonists
- GnRH antagonists
- Adjuvant pain medications
- Analgesic drugs
- Pituitary and hypothalamic hormones and analogues
- Sex hormones and modulators of the genital system
- Anti-inflammatory drugs
- Acetylsalicylic acid and its salts

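### SAP Section 6.1.7 lists hormonal drug classes under a nonhormonal heading, so the separate group B medication summary could count a hormone-only user as a user of nonhormonal treatment

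*SAP*

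**What the plan says.** Section 6.1.7 of the SAP deals with group B medication in three consecutive steps.

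- It says what is collected: "Nonhormonal medical treatment for symptomatic uterine fibroids at/after the date of randomization for treatment group B will be recorded and coded to ATC codes".
- It defines a separate summary: "Subjects in treatment group B who took at least one nonhormonal symptomatic medical treatment will be summarized for prior/concomitant/post-treatment medications separately".
- It then gives a list of drug classes headed with the same term, "nonhormonal symptomatic medical treatment" (capitalised, with a colon).

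Most entries are pain, antidepressant, sedative, haemostatic or anti-inflammatory classes. The list also contains "GnRH agonists", "GnRH antagonists", "Pituitary and hypothalamic hormones and analogues" and "Sex hormones and modulators of the genital system". No footnote, subheading or exclusion rule separates these four from the rest.

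For all groups, Section 6.1.7 adds: "The number of subjects taking prior or concomitant medication will be analyzed using frequency tables based on classified data". Those tables are on the SAF, and Section 4.1 has tables show each randomized group, including B. The introduction to Section 6.1 provides, in general, for descriptive statistics and listings of the variables defined there.

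Sections 2 and 3 describe the comparator as nonhormonal. The Figure 3-1 legend gives group B symptomatic nonhormonal treatment chosen by the investigator and/or watchful waiting.

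**The concern.** The list comes directly after the rule, uses the rule's own term, and is the only definition of that term in the SAP. A programmer would therefore take it as the specification. Read that way, it places classes named as hormones in a category called nonhormonal.

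The separate summary tells the reader which symptomatic drugs the comparator group actually took. Its entry condition is at least one drug from the list, so a single hormonal drug could be enough to enter. A table meant to describe nonhormonal care could then include hormone use without labelling it. What is at stake is whether that count and its label are correct. The treatment comparison is not at stake.

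**Working it through.** The SAP gives no figure to reproduce here. The check is a count of list entries and a comparison of sections.

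**Count of entries (labels, not subjects)**

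- Total entries under the heading: 23.
- Entries whose names contain the word hormones: 2 (the pituitary/hypothalamic class and the sex-hormone class).
- GnRH entries: 2 (agonists and antagonists). The SAP does not expand this abbreviation. Treating them as hormonal rests on ordinary pharmacological usage.
- Remaining if only the two self-named entries are set apart: 23 − 2 = 21.
- Remaining if all four are set apart: 23 − 2 − 2 = 19.

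The contradiction already stands on the first two entries. The GnRH entries affect only whether 21 or 19 remain.

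**Heading against list.** The heading says nonhormonal, and at least two entries are hormones by their own names. Nothing in the SAP explains this.

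**List against comparator.** Sections 2 and 3 describe group B care as nonhormonal. The list used to summarize that care admits hormonal classes.

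**Applying the rule.** Take a group B subject with one listed drug, a sex hormone. The drug is on the list, so the condition of at least one is met and the subject is counted as having taken nonhormonal treatment. This holds unless something upstream removes the drug.

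**Is there an upstream filter?** The sentence on collection says that nonhormonal treatment is what is recorded for group B. If that record alone feeds the summary, such a subject might never enter. The SAP does not say that it does. That record is also limited to treatment at or after randomization, whereas the summary covers prior medication as well. For group B, prior means before the randomization date (Section 4.5 with Section 6.1.7). A drug that ended before randomization could not come from that record, so another source may be used. This makes a complete filter uncertain but does not rule it out.

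**Does the list reach any other analysis?** Under Section 5.1 all subjects randomized to group B enter the FAS and the SAF, whatever medication they took. The modified SAF depends on validity findings specified in a separate document, and the SAP does not tie them to this list. The BMD analysis (Section 6.5.1) and the analysis of bleeding days (Sections 4.5 and 6.2.2) do not refer to it.

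**The case against.** The strongest counter-argument is that the SAP says only nonhormonal treatment is recorded for group B. The list would then merely classify drugs already accepted as nonhormonal. This is possible, and for that reason it cannot be said that hormone-only users *will* be miscounted, only that they *could* be. It does not rescue the text, because if hormonal drugs never enter, the hormonal entries have no function under this heading.

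Second, broad drug classes may contain nonhormonal members, or the list may be a deliberately wide set of symptomatic drugs under a poorly chosen heading. The SAP does not show whether the heading or the list is at fault. That argues for allowing either correction, but not for leaving the two in conflict.

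Third, hormone use in group B should be visible elsewhere. This largely stands. The general prior and concomitant tables are shown by group, and Section 6.1 provides for listings. The sentence on general frequency tables does not mention post-treatment medication, but Section 6.1.7 defines that category, so the general provision in Section 6.1 covers it. A correct entry elsewhere still does not correct a wrong label in this summary.

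A reader might also infer that the plan permits hormonal treatment in group B, or that the BMD or bleeding comparison is contaminated. The SAP supports neither inference. The list groups medications for a table. It does not say what subjects may take, and no estimate is computed from it.

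**Conclusion.** The inconsistency is real and **minor**. Two entries contradict the heading by name, and two more do so if GnRH classes are taken as hormonal. As written, the separate group B summary could report a hormone-only user as a user of nonhormonal treatment. This assumes that the list is the working definition of the term and that recording does not already exclude hormonal drugs. The SAP leaves the second point open.

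The number of subjects affected cannot be derived from the SAP and may be zero. The list has no effect on the BMD or bleeding-day estimates, and the SAP links no analysis set to it. It would go too far to conclude that hormone use in group B would be hidden.

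**What to change.** Reconcile the heading and the list in Section 6.1.7.

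- **Preferred:** base the nonhormonal count on the list without the hormonal classes (19 of 23 entries). Show the four classes for group B under a separate hormonal label in the same table. If a class was included because of a nonhormonal member, name that member.
- **Alternative:** rename both the list and the summary as symptomatic medical treatment, dropping the word nonhormonal, and show hormonal and nonhormonal rows separately.

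It would also help to state which medication record feeds this summary, since that settles whether hormonal drugs can enter at all.

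The cost is an edit to one medication grouping and a few labelled rows in a descriptive table that is already planned. No analysis set, estimate or confidence interval changes.
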